10.4.2 Analysis of the Primary Endpoints

Hypothesis 1: The rate of follow-up suicidal behavior will be significantly reduced among military personnel receiving CRP versus usual care risk management in addition to massed CPT.

Survival analysis with time-to-suicide attempt will be used to test overall differences between the two intervention groups. We will use the hazard ratio derived from the Cox regression supplemented with the log-rank and Wilcoxon statistics derived from the Kaplan-Meier method. Time will be calculated as number of days since the intake appointment. Multiple suicide attempts within participants will be handled using the Andersen-Gill counting process model (Anderson & Gill, 1982), which assumes that the time increments between multiple suicide attempts can be explained by past suicide attempts (e.g., shorter time intervals between suicide attempts are more likely among patients who have previously attempted suicide). **Power Analysis:** Power calculations for H1 were conducted using PROC POWER in the SAS 9.4 software. Anticipated suicide attempt rates were based on previously published clinical trials conducted within and external to the military. In previous studies of cognitive behavioral therapies for suicide prevention, the suicide attempt rate in the usual care conditions often ranges from 40-50% during the first year and active suicide-focused interventions typically have 50% lower suicide attempt rates (Brown et al., 2005; Gysin-Maillart et al., 2016; Linehan et al., 1991; Rudd et al., 2015). In our previous RCT of CRP versus usual care ([name] et al., 2017), participants receiving CRP were 76% less likely to attempt suicide. Results of our pilot study of massed CPT yielded a similar 73% reduction in suicide attempts in the CRP group versus usual care. We therefore estimated statistical power for hazard ratios ranging from 0.50-0.75 when suicide attempt rates in usual care ranged from 30-50%, assuming 15% attrition, 1-year follow-up, and a two-tailed $p<.05$. $N=150$ yielded $>80\%$ power under nearly all conditions.

Hypothesis 2: Reductions in the severity of suicidal ideation will be significantly larger among military personnel receiving CRP versus usual care risk management.

Mixed effects regression models with repeated measures will be used to test group differences in suicidal ideation over time. Treatment group, time, and the treatment*time interaction will be entered as independent variables and SSI scores as the outcome. Random intercepts and slopes will be tested, and covariance structures will be selected by comparison of likelihood criteria (e.g., Akaike's Information Criteria). Group differences in mean SSI scores will be probed at 2, 4, 13, 26, 39, and 52 weeks, with the largest differences between groups expected to occur at 2 and 4 weeks. Consistent with these expectations, we will also compare the SSI slopes from baseline to session 5 (treatment midpoint) and session 10 (treatment end) to determine if the rate of change in suicidal ideation differs across groups.

Power Analysis: We used the General Linear Mixed Model Power and Sample Size (GLIMMPS) software to calculate power for H2 using data from our pilot study to estimate SSI mean differences between groups at baseline ($M_{diff}=0$), treatment midpoint ($M_{diff}=4$), and treatment end ($M_{diff}=2$) assuming a two-tailed $p<.05$. Results indicated $N=150$ provided 81% power.

Hypothesis 3: Less severe suicide risk features during treatment will predict treatment response (i.e., change in severity of suicidal ideation) and treatment relapse (i.e., follow-up suicidal behavior).

For H3, we will use suicidal ideation EMA ratings collected during the 2 weeks of massed CPT. We will first calculate the following indices of change in suicidal ideation during the entire 2-week observation

Abbreviated Title: mCPT+CRP

Version Date: 07/10/25

window (up to 42 EMA surveys per participant) for each participant: stability (i.e., the autocorrelation of scores over time), severity (i.e., mean score across all responses), and variability (i.e., the root mean square successive difference [RMSSD] across all responses). Each change index will be entered as an independent variable into a linear regression model predicting pre-post change in SSI score and a binary logistic regression model predicting follow-up suicidal behavior. To evaluate the specificity of these findings to the two weeks of active treatment, we will expand these analyses to include all 5 weeks of planned EMA data collection (i.e., 1 week prior to treatment start, 2 weeks of treatment, 2 weeks after treatment completion). This approach will allow us to distinguish treatment-specific patterns from more general patterns that signal treatment response and treatment relapse. **Power Analysis:** Power calculations for H3 were conducted using G*Power 3.1.9.2 (for suicidal ideation) and PROC POWER in the SAS 9.4 software (for suicide attempts). For the linear regression model, N=150 yielded 80% power to detect a medium effect ($R^2=0.06$) and for the binary logistic regression, N=150 provided >80% power to detect an odds ratio=1.5, assuming a conservative 20% of participants attempts suicide during follow-up.

Exploratory Research Question 1: Which subjective, objective, and treatment-related factors are most useful for predicting treatment response (i.e., change in severity of suicidal ideation) and treatment relapse (i.e., follow-up suicidal behavior)?

We will use the same analytic approach described for H3 but extend the analyses to all other variables assessed via EMA (i.e., positive and negative affect, negative thinking, and maladaptive behaviors) and Fitbit (i.e., physical activity, sleep quality). We will construct a series of models to determine which variables (and combination of variables) maximize the variance explained in pre-post change in SSI score and follow-up suicidal behavior. **Power Analysis:** Power calculations for RQ1 were conducted using G*Power 3.1.9.2. Assuming our model includes no more than 6 predictor variables, N=150 yielded 80% power to detect R^2 increases of 0.06-0.08 associated with each additional predictor variable.

Hypothesis 4: More frequent CRP use will be correlated with reductions in suicide attempts and suicidal ideation.

We will sum the number of EMA responses during which participants endorsed the use of their CRP (and safety plan), such that higher values indicate more frequent intervention use. This count variable will be entered into a Cox regression model predicting time to suicide attempt and a linear regression model predicting change in SSI score to assess the correlation of intervention use with, respectively, follow-up suicidal behavior and severity of suicidal ideation. We will construct separate models for each treatment group. To test the specificity of our findings to CRP, we will repeat these analyses with CPT homework completion, also assessed during EMA and calculated as the sum of positively endorsed EMA responses, entered as a covariate. **Power Analysis:** The power analysis for H4 mirrors the power analysis for H3 above.

Exploratory Research Question 2: Which treatment components and design features do participants find most helpful for reducing suicidal ideation and attempts?

We will use descriptive statistics of participant characteristics, chi-squared tests, and Pearson correlations (where applicable) to explore relationships among personal experiential themes, group experiential themes, and participant characteristics. **Power Analysis:** Recommendations for minimum sample size in qualitative studies using IPA typically range from 2-25 participants, depending on the homogeneity that exists within participants' lived experience (Alase, 2017; Smith et al., 1999). Because we plan to interview all enrolled participants, our sample size will be more than adequate.

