10.4 STATISTICAL ANALYSES

10.4.1 General Approach

Prior to statistical analyses, data will be screened to assess the need for scale transformations (e.g., log, reciprocal) to normalize distributions or reduce variance heterogeneity. The study design is a two-arm randomized clinical trial with a superiority hypothesis (i.e., CRP superior to usual care). Analyses will use survival analysis and mixed effects regression with repeated measures. Follow-up assessment data will be collected from participants even if they drop out of therapy early. The primary focus will be on

Abbreviated Title: mCPT+CRP

Version Date: 07/10/25

group differences over time. All hypotheses will be two-sided at the $\alpha=.05$ level. Little's MCAR test will be used to determine if data are missing at random (Li, 2013; Little et al., 2002) and random effects pattern-mixture modeling will be used to determine if missingness influences longitudinal results (Hedeker & Gibbons, 1997; Little, 1993). The principal statistical software to be used is SAS 9.4 supplemented with SPSS, R, and MPlus.

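### The H1 text credits the Andersen-Gill model with a dependence on past attempts that the model as named leaves out, so with model-based variance the recurrent-event test would exceed its .05 level

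*Protocol*

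**What the plan says.** Protocol section 10.4.2 tests H1 first by time to suicide attempt: "We will use the hazard ratio derived from the Cox regression supplemented with the log-rank and Wilcoxon statistics". It then adds: "Multiple suicide attempts within participants will be handled using the Andersen-Gill counting process model", "which assumes that the time increments between multiple suicide attempts can be explained by past suicide attempts". Its example is that "shorter time intervals between suicide attempts are more likely among patients who have previously attempted suicide". The time scale is total time: "Time will be calculated as number of days since the intake appointment".

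No prior-attempt term, event-order stratum, frailty term or clustered variance is named. Section 10.4.1 sets the error rate ("All hypotheses will be two-sided at the" .05 level) and the software ("The principal statistical software to be used is SAS 9.4 supplemented with SPSS, R, and MPlus"). The H1 power paragraph gives the planning range used below: "when suicide attempt rates in usual care ranged from 30-50%, assuming 15% attrition, 1-year follow-up".

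**The concern.** The sentence gives a property of the model as the reason it can handle repeat attempts, and the model does not have that property as specified. In Andersen-Gill, event history acts on the intensity only through covariates that the analyst enters. Without such a term every attempt, first or later, shares one baseline intensity, and increments are taken as independent given the covariates. The protocol therefore expects a dependence and names a model that ignores it.

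The point estimate can still be read as a ratio of attempt rates. The usual standard error is the weak point. When some participants contribute clusters of attempts, counts vary more than the model allows, the model-based standard error is too small, and the test exceeds .05. A reader who takes the clause at face value would see no reason to correct this. H1 is the primary hypothesis, it is worded as a rate, and the pilot reduction cited for it is itself on the per-person attempt scale: (7/41)/(21/33) = 0.268, the 73.2% in section 4.3.

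**Working it through.** **Inputs from the protocol.** N = 150, taken as 75 per arm; two-sided .05; 1-year follow-up; 15% attrition; 30%, 40% or 50% attempting within a year.

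**Assumptions.** The protocol gives no size for the dependence. Two forms were used: the hazard is multiplied by *r* after a first attempt (the mechanism the protocol describes), or participants differ by a gamma frailty with mean 1 and variance θ. The model has treatment only, with variance from the partial likelihood.

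**Hand check without attrition.** Under the null with everyone followed for the year, the true variance of the Andersen-Gill score divided by its model-based variance equals Var(N)/E(N), where N is attempts per person. Actual two-sided error is then 2·[1 − Φ(1.96/√ratio)].

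For a rise of *r*, with h = −ln(1−p), A = r(h−p) and B = r²[h² − 2(h−p)]:

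- E(N) = p + A
- E(N²) = p + 3A + B

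For p = 0.40 and r = 2: h = 0.5108, A = 0.2217, B = 0.1572. So E(N) = 0.6217, E(N²) = 1.222, Var(N) = 1.222 − 0.6217² = 0.836. The ratio is 1.344, its root 1.159, and the error 2·[1 − Φ(1.690)] = 0.091.

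For frailty the ratio is (1−p)^(−θ). At p = 0.40 and θ = 1 it is 1.667, giving 0.129.

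**Simulation with attrition.** 10,000 null trials per cell (Monte Carlo standard error about 0.002 at 0.05); 15% censored uniformly over the year, the rest at 1 year. Entries are for 30/40/50% attempting.

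| Dependence | Hand formula, no attrition | Simulated, model-based variance |
|---|---|---|
| none (r = 1) | 0.050/0.050/0.050 | 0.046-0.051 |
| r = 2 | 0.082/0.091/0.099 | 0.074/0.084/0.099 |
| r = 3 | 0.112/0.128/0.142 | 0.110/0.125/0.134 |
| r = 4 | 0.139/0.161/0.179 | 0.132/0.152/0.174 |
| θ = 0.5 | 0.073/0.085/0.099 | 0.064/0.076/0.097 |
| θ = 1 | 0.101/0.129/0.166 | 0.099/0.121/0.160 |
| θ = 2 | 0.170/0.240/0.327 | 0.165/0.232/0.323 |

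The planned .05 is reproduced when attempts are independent, and only then. At p = 0.40 and r = 2 about 56 of 150 participants attempt and 22 repeat, so the inflation does not need an extreme scenario.

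**Comparators in the same simulation.** Participant-clustered sandwich variance gives 0.048-0.055 for r = 2 to 4 and 0.050-0.061 under frailty. First-attempt Cox gives 0.043-0.051 throughout.

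**Second simulation.** With exponential dropout and 4,000 trials per cell, r = 2 gave 0.079/0.080/0.105 and r = 3 gave 0.111/0.117/0.150. At 50% attempting and r = 3, the mean model-based standard error was 0.166, against an empirical standard deviation of 0.226 and a mean robust standard error of 0.219.

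**Are repeat attempts likely here?** Pilot usual care had 21 attempts in 33 people by 6 months, 0.64 each. A 50% one-year risk with independent attempts implies 0.693/2 = 0.35 in 6 months. The samples differ, so this is only indicative.

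**The case against.** The strongest reply is that the clause is a loose account of a conditional assumption. Andersen-Gill can carry event history. With a time-dependent any-prior-attempt term and model-based variance, the level holds under pure event dependence: 0.051 at r = 2 and 0.053 at r = 4, both at 40% attempting. On this view only the term is missing, and covariate lists and variance estimators may be left to a statistical analysis plan.

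Part of this stands. The fault lies in the specification and wording, not in the framework. The protocol does not say the variance will be model-based, and that choice alone could wait. But the history term does not rescue the text. Without clustering it fails under frailty (0.074 to 0.128 in the cells run). It also conditions on attempts made after randomisation, which treatment can change, so the treatment coefficient no longer estimates the same effect. Leaving a detail open also differs from stating a wrong reason why no detail is needed.

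Three further points have weight:

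- The size depends wholly on an assumed dependence.
- The protocol does not make clear whether the first-attempt or the recurrent-event result decides H1, so harm to the primary conclusion is possible but not shown.
- Previous attempts might be read to include those before enrolment. A baseline history covariate would escape the post-randomisation objection and could absorb some heterogeneity. None is named, however, and the sentence is about multiple attempts within participants.

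**Conclusion.** The concern holds as a conditional one. The stated assumption is wrong for the model as named, whatever the variance estimator. The inflation follows if three things coincide: no history term, model-based variance, and the dependence the protocol expects. Under its own mechanism the two-sided error is then about 0.07 to 0.17 for a 2- to 4-fold rise. Under frailty variance of 0.5 to 2 it is 0.064 to 0.323. There is no inflation if attempts are independent, and the first-attempt Cox, log-rank and Wilcoxon results are untouched. This should be corrected, but it does not invalidate H1. It does not depend on the H1 power statement, which was not used here.

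**What to change.** Replace the clause with the correct assumption: increments are independent given the covariates in the model. Add that the Andersen-Gill treatment hazard ratio will use a sandwich variance clustered on participant (in SAS 9.4, PROC PHREG with COVS(AGGREGATE) and an ID statement). Do not enter post-randomisation attempts as a covariate in the model that estimates the treatment effect.

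The cost is one sentence and one software option. Under the null the standard error is essentially unchanged with independent attempts (factor 0.99). It widens by 1.11-1.17 for a 2-fold rise, 1.21-1.32 for 3-fold, 1.30-1.44 for 4-fold, and 1.07-1.92 for frailty variance 0.5 to 2. At a per-attempt ratio of 0.50 with a 2-fold rise, rejection falls from 63/80/92% to 56/75/88% at 30/40/50% attempting, but the higher figures come from a test that does not hold its level.

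The robust test is not exact at this sample size. It reached 0.061 under strong frailty, and 0.069 in the second simulation when a 3-fold rise and frailty variance 1 were combined.

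### The H2 mixed model estimates a separate baseline SSI mean for each randomised arm and does not adjust for baseline SSI, so it gives up precision the trial already has

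*Protocol*

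**What the plan says.** Section 10.4.2 (Hypothesis 2) names the fixed effects: "Treatment group, time, and the treatment*time interaction will be entered as independent variables and SSI scores as the outcome". Only the random effects and the covariance are left open: "Random intercepts and slopes will be tested, and covariance structures will be selected by comparison of likelihood criteria". That choice does not alter the mean model.

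Two sets of contrasts follow. The first is visit means: "Group differences in mean SSI scores will be probed at 2, 4, 13, 26, 39, and 52 weeks". The second is early change: "we will also compare the SSI slopes from baseline to session 5 (treatment midpoint) and session 10 (treatment end"). The slopes start at baseline, and the H2 power calculation has a baseline occasion with a mean difference of 0, followed by 4 at mid-treatment and 2 at treatment end. Baseline SSI is therefore part of the outcome series.

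The protocol nowhere enters baseline SSI as a covariate or constrains the arms to a common baseline mean. The Schedule of Events (section 1.2) collects SSI at BL and at every later visit. Section 6.1 uses an SSI item for eligibility, and section 9.2.1 randomises only after eligibility is confirmed. The BL score therefore precedes allocation.

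**The concern.** A group main effect plus a group-by-time interaction leaves the baseline means of the two arms free to differ. Randomisation guarantees that they do not differ in expectation. Estimating that difference has two consequences:

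- With complete data, each probed visit difference (2 to 52 weeks) is a raw difference of means. It takes nothing from baseline and carries whatever chance imbalance occurred.
- The interaction and slope contrasts use baseline only through change scores, which are in general less precise than adjustment.

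H2 is the trial's only between-arm hypothesis on suicidal ideation. Its planned power of 81% has little reserve, and the protocol states an attrition allowance for H1 (15%) but none for H2.

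**Working it through.** **Inputs from the protocol.** Mean SSI differences d = (0, 4, 2) at baseline, mid-treatment and treatment end; N = 150; two-sided alpha 0.05; stated power 81%.

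**Assumptions.** 75 per arm. The protocol gives no SSI SD and no correlation; it refers only to "using data from our pilot study to estimate SSI mean differences between groups". I take rho from 0.4 to 0.7, equal variance at each occasion, and compound symmetry (CS) or AR(1) correlation. I also assume that the 81% refers to the 2-df group-by-time test, because the protocol does not say which test was evaluated.

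**Step 1: the protocol's figure.** Without SD and rho, 81% can be neither reproduced nor refuted. It can only be inverted. A 2-df F test at alpha 0.05 has 81% power at noncentrality λ = 10.07. With n per arm and C forming the two changes from baseline,

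λ = (n/2)(Cd)′(CΣC′)⁻¹(Cd).

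Under CS this reduces to λ = (75/2) × 8/[(1 − rho)SD²] = 300/[(1 − rho)SD²]. At rho = 0.5, SD² = 300/(0.5 × 10.07) = 59.6, so SD = 7.72.

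**Step 2: same inputs, common baseline mean.** The noncentrality becomes λ = (n/2)d′Σ⁻¹d. Under CS this is

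λ = (75/2) × [20 − 36·rho/(1 + 2·rho)]/[(1 − rho)SD²],

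so the ratio to Step 1 is [20 − 36·rho/(1 + 2·rho)]/8. At rho = 0.5 the ratio is (20 − 9)/8 = 1.375, and λ = 10.07 × 1.375 = 13.85.

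| rho | SD giving 81% (CS) | λ, common baseline (CS) | Power (CS) | SD giving 81% (AR(1)) | Power (AR(1)) |
|---|---|---|---|---|---|
| 0.4 | 7.05 | 15.11 | 94% | 7.20 | 92% |
| 0.5 | 7.72 | 13.85 | 92% | 7.97 | 89% |
| 0.6 | 8.63 | 12.82 | 90% | 9.02 | 87% |
| 0.7 | 9.96 | 11.96 | 88% | 10.57 | 84% |

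**Step 3: single contrasts.** With complete data and equal variances, the variance under the common-baseline model is a fraction of that under the stated model:

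- visit mean difference: 1 − rho²
- change-from-baseline contrast: 2(1 − rho) falls to 1 − rho², a ratio of (1 + rho)/2

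| rho | Visit mean ratio | Equivalent unadjusted N | Change contrast ratio |
|---|---|---|---|
| 0.3 | 0.91 | 165 | 0.65 |
| 0.4 | 0.84 | 179 | 0.70 |
| 0.5 | 0.75 | 200 | 0.75 |
| 0.6 | 0.64 | 234 | 0.80 |
| 0.7 | 0.51 | 294 | 0.85 |

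The equivalent N is 150 divided by the visit mean ratio. A generalised least squares information matrix for eight visits (BL and weeks 1, 2, 4, 13, 26, 39, 52; random-intercept correlation) returned these ratios. With 15% dropout they barely move: 0.913 to 0.520 for week 2 and 0.660 to 0.855 for change, over rho 0.3 to 0.7.

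**The case against.** **It is not an error.** The stated model is a standard repeated-measures specification, unbiased under randomisation and with correct type I error. That is true. The point concerns efficiency. It still belongs in a protocol review because the protocol itself writes out the mean model instead of leaving it to the SAP.

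**The interaction already removes baseline imbalance.** It does, but by differencing. The large savings at high rho apply to the visit means. For the interaction, the saving at rho 0.7 is 15%, not 49%. The two savings run in opposite directions with rho and should not be quoted as if both were large.

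**The factor (1 + rho)/2 needs equal variances.** This also stands. If the baseline SD is k times the follow-up SD, the ratio is (1 − rho²)/(1 + k² − 2·rho·k). At k = 0.7 and rho = 0.5 it is 0.75/0.79 = 0.95, a saving of only 5%, and at k = rho there is no saving. But the denominator minus the numerator is (k − rho)², which is never negative, so adjustment never does worse. Selecting patients on an SSI item could also restrict the baseline range and lower rho. At rho 0.3 the visit-mean saving is 9%.

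**The fix depends on how time is coded.** If time were a straight line, deleting the group main effect would force the arm difference to grow linearly from zero. That conflicts with the protocol's expectation of the largest differences at 2 and 4 weeks. This limits how the constraint is written but does not defeat it: it can be stated for the BL visit with time categorical, and the covariate form works under either coding.

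**The primary outcome is suicidal behaviour.** Correct; the H1 conclusion is unaffected.

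**Conclusion.** The concern holds. The stated H2 model spends information on a baseline difference that is zero by design. The conclusions remain valid but the standard errors are larger than they need be. Under equal variances and rho 0.4 to 0.7, the variance of a visit difference could fall by 16–49% and that of a change contrast by 30–15%. The test with stated power of 81% would have about 84–94%. The power figures also rest on the 2-df reading of the 81% and on SDs solved to match it. The direction does not depend on these assumptions: a common baseline or baseline adjustment is never less precise in large samples. This is a change that should be made, but H2 is not invalid without it.

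**What to change.** Restate the H2 model in section 10.4.2 in one of two ways:

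- **Preferred:** keep BL SSI in the outcome vector, code visit as categorical, and include arm effects at post-baseline visits only, so that both arms share one BL mean (constrained longitudinal data analysis). This retains participants who have no post-baseline SSI.
- **Alternative:** model post-baseline SSI with BL SSI, and BL SSI by time, as covariates.

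Use the BL score, not the intake score, because the arm assignment is made known at the intake appointment. Take all six visit contrasts and the early-change comparisons from this one model. When revising, restate the H2 power with its SD, correlation, attrition and the test evaluated.

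The cost is a sentence of model wording and an explicit choice of time coding. It needs no extra patients, visits or data. It should be specified before any outcome data are seen by arm.
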